4.2.3.3 Discontinuation of Study Participation Due to the Death of a Subject

If a subject dies, the subject will be deemed to have been withdrawn from study participation at the time of death. The investigator or subinvestigator will survey information such as the date and time of death and the reason for the death according to "6.14 Efficacy Events" and enter the information on the case report form.

4.2.3.4 Termination of the Entire Study by Sponsor

If the Sponsor decides to terminate the entire study according to the regulations specified in "15.8.1 Termination or Interruption of the Study," the investigator or subinvestigator will promptly withdraw subjects from the study and take the suitable action for subjects in response. The investigator or subinvestigator will perform follow-up survey of abnormal findings at the time of discontinuation, and as far as the subjects (or legally acceptable representatives) are willing to cooperate, will perform the examination at discontinuation and make every attempt to ensure the safety of subjects, and will enter the date of discontinuation and the reason for discontinuation on case report forms.

5. METHODOLOGY

5.1 Study Drug

Details of the study drug and how to handle it are available in the Investigator's Brochure and Study Drug Management Procedures.

5.1.1 Investigational Product

1) Code name: DU-176b

2) Generic name: edoxaban tosilate hydrate

- 3) Content and dosage form: Yellow film-coated tablets containing 15 mg of edoxaban per tablet
- 4) Lot number: Please refer to the Study Drug Management Procedures

5.1.2 Placebo

- Content and dosage form: Yellow film-coated tablets not containing any active ingredient, with an appearance (shape, color, and odor) indistinguishable from that of the Investigational Product
- 2) Lot number: Please refer to the Study Drug Management Procedures
- 3) Provider: Daiichi Sankyo Co., Ltd.

5.1.3 Labeling and Packaging

The packaging of the study drug and the contents of labels are shown in the Study Drug Management Procedures.

5.1.4 Study Drug Accountability

After concluding a study contract, the Sponsor will dispense the study drug to the study site. The study drug managers will store the drug at room temperature and manage it. Management and collection of the study drug will be performed according to the Study Drug Management Procedures.

5.2 Study Treatments Administered

5.2.1 Dose and Route of Administration

After randomization, study treatment will be started on the same date that notification of study drug identifiers is given. One tablet of DU-176b 15 mg or placebo will be administered orally once daily. Administration of the study drug will be continued until the examination at completion of study treatment performed within 60 days after the declaration of completion of the study. Completion of the study will be declared when the planned number of subjects with primary efficacy endpoint events (stroke and SEE) has been collected. The planned mean duration of study treatment is 2 to 2.5 years. When the investigator or subinvestigator requires to know the study treatment assignment for each subject to determine the subsequent treatment after the final administration of the study drug, the study treatment can be continued until the final follow-up examination (in principle, within a month after notifying their study treatment assignments) after obtaining consent from the subject. The planned duration of the additional study

treatment from the examination at completion of study treatment to the final follow-up examination is 3 to 4 months.

<Rationale>

For the DU-176b group, a dosage of 15 mg once daily was selected, so that it is expected to be effective at reducing the risk of stroke, and so that the bleeding risk is lower than that for the approved edoxaban dosage.

In a phase 3 global study of DU-176b in patients with NVAF (ENGAGE AF-TIMI 48), the annual incidence of composite of stroke and SEE with administration of edoxaban at 15 mg once daily was 2.36%/year for the overall population and 2.79%/year for the Japanese population (2.21%/year and 1.20%/year respectively, in the warfarin group). At present, due to changes in the medical environment, the incidence of events such as these may have decreased, but in meta-analysis using data from randomized clinical studies of VKAs conducted in patients with AF in the past, it was reported that the annual incidence of non-fatal stroke in the control group (untreated) was 7.6%/year (2.5%/year in the VKA group). Given this, from the results of the ENGAGE AF-TIMI 48 study, it is expected that even if edoxaban is administered at 15 mg once daily, it will be effective at reducing the risk of stroke to a certain extent, based on its anticoagulant effect. The annual incidence of composite of stroke and SEE during administration of edoxaban at 15 mg once daily in subjects aged 80 years or older in the ENGAGE AF-TIMI 48 study was 2.33%/year for the overall study population, which is similar to the result (2.36%/year) for all subjects administered 15 mg once daily regardless of age. In addition, in the AVERROES study¹⁶ evaluating the efficacy of apixaban in patients with AF and VKA is not indicated, the annual incidence of composite of stroke and SEE in the aspirin group, which was the control group, was 3.7%/year, and thus the annual incidence during administration of edoxaban at 15 mg once daily in the ENGAGE AF-TIMI 48 study was lower than this. Aspirin is not positioned as a standard of care for reducing the risk of stroke in patients with AF, and is not recommended as antithrombotic therapy in patients with AF⁶, but it is expected that administration of edoxaban at 15 mg once daily will show a greater reduction of the risk of stroke than aspirin.

From the safety standpoint, no hemorrhagic stroke was found during administration of edoxaban at 15 mg once daily in the ENGAGE AF-TIMI 48 study, and the annual incidence of intracranial hemorrhage was 0.14%/year, lower than the incidence in the warfarin group of 1.26%/year, and also lower than the incidence of 0.57%/year in subjects administered edoxaban at 30 mg once daily due to dosage adjustment. The

annual incidence of major bleeding was 1.50%/year with administration of edoxaban at 15 mg once daily, which was lower than the incidences of 4.85%/year in the warfarin group and 3.05%/year with administration of dosage-adjusted edoxaban at 30 mg once daily. In addition, even if analysis is restricted to subjects aged 80 years or older in the ENGAGE AF-TIMI 48 study, the annual incidence of major bleeding was 1.99%/year with administration of edoxaban 15 mg once daily, 6.77%/year in the warfarin group, and 4.28%/year with administration of dosage-adjusted edoxaban at 30 mg once daily, showing that even in elderly patients with AF, the bleeding risk from administration of edoxaban at 15 mg once daily is lower than that of warfarin or of edoxaban at the approved dosage.

Thus, administration of edoxaban at 15 mg once daily is associated with a lower bleeding risk than the available oral anticoagulant warfarin or administration of edoxaban at 30 mg or 60 mg once daily, and from the efficacy standpoint, it is considered to be effective at reducing the risk of stroke to a certain extent. Therefore, administration at 15 mg once daily was selected as the dosage in the DU-176b group of this study.

5.2.2 Randomization and Blinding

5.2.2.1 Method of Assigning Subjects to Treatments

An independent biostatistician will prepare a randomization schedule in accordance with the Sponsor's directions. Based on the information entered into IRT, subjects will be assigned to the DU-176b group or placebo group in a 1:1 ratio using a stratified randomization method with the CHADS₂ index score (≤ 2 points, ≥ 3 points) as a factor.

5.2.2.2 Blinding

This study will be a double-blind study, and blinding will be performed for all related parties (subjects, investigators, and the Sponsor) other than the independent biostatistician, those involved in assignment and packaging of the study drug and quality assurance, and those relating to the drug concentration measurement laboratory.

5.2.2.3 Unblinding Procedure for Emergencies

5.2.2.3.1 If the Investigator or Subinvestigator Considers That Unblinding Is Absolutely Necessary

If the investigator or subinvestigator considers that information on which treatment group a subject belongs to is absolutely necessary to treat an adverse event, the investigator or subinvestigator will unblind using IRT.

5.2.2.3.2 If a Serious Adverse Event Occurring in This Study Is Reported to the Regulatory Authority

The assigned person for limited unblinding of safety information will unblind using IRT.

5.2.2.4 Unblinding Procedure

When items 1), 2), and 3) below have been checked and it has been considered that there are no problems, the Sponsor will unblind.

- 1) The database has been locked.
- 2) The analysis plan has been finalized.
- 3) The decisions on whether or not to include subjects in analysis sets and on the handling of data have been finalized.

5.3 Prohibited Concomitant Medications and Prohibited Tests

5.3.1 Prohibited Concomitant Medications

Between the time of informed consent and the final dose of study drug (excluding the follow-up survey periods during study drug interruption and after study drug discontinuation), concomitant administration of anticoagulants or thrombolytic drugs will be prohibited. Mono antiplatelet therapy (including over-the-counter drug containing aspirin) will be permitted only when administered to treat concurrent diseases, but concomitant administration of antiplatelet therapy to reduce the risk of cardioembolic stroke based on AF will be prohibited.

If it becomes necessary to administer prohibited concomitant medications after the initiation of study treatment, the treatment will be interrupted (see "4.2.1 Study Drug Interruption").

<Rationale>

Concomitant administration of anticoagulants, antiplatelet drugs to reduce the risk of cardioembolic stroke based on AF, and thrombolytic drugs has been prohibited in this study because these drugs will affect the efficacy assessment of the study drug. As concomitant administration of dual or multidrug antiplatelet therapy causes a particularly large increase in bleeding risk, it has also been prohibited, to ensure the safety of subjects.

5.3.2 Prohibited Tests

To ensure blinding, tests affecting blinding will be prohibited at the study site from the initiation of study treatment until 2 days after the day of the examination at completion of study treatment (excluding the duration of follow-up at least 3 days after the date of study drug discontinuation or the date of study drug interruption) or the final follow-up examination (when the study treatment is continued after the examination at completion of study treatment), such as the following: pharmacodynamic (PD) indicator tests (prothrombin time [PT], activated partial thromboplastin time [aPTT]), and biomarker tests (D-dimer, prothrombin fragment 1+2 [F1+2], activated coagulation factor X [Xa]). However, cases where testing is unavoidable, for example to treat an adverse event or in an emergency, will be permitted. Whether PD and biomarker tests were performed during the period from the initiation of study treatment to the day of the examination at completion of study treatment, the date of conduction of these tests, and the concerned test items will be recorded on case report forms.

6. STUDY PROCEDURES

6.1 Study Procedure and Specimen Collection Schedule

The timing of study procedures and specimen collection in this study is shown in Table 6-1. The investigator or subinvestigator will record information such as the results of study procedures, the dates and times of specimen collection, the state of specimens at the time of sampling, and comments about these.

The examination at completion of study treatment will be performed within 60 days after the declaration of completion of the study, including subjects for whom study treatment has been interrupted or discontinued. Completion of the study will be declared when the planned number of subjects with primary efficacy endpoint events (stroke and SEE) has been collected.

The final follow-up examination will be performed within the 30 to 37 days after the examination at completion of study treatment. For subjects who continue the study treatment after the examination at completion of study treatment, the final follow-up examination will be performed, in principle, within a month after notifying their study treatment assignments.

Follow-up survey of subjects for whom study treatment has been interrupted or discontinued will be performed according to "4.2.1.2 Follow-up Survey During Study Drug Interruption" and "4.2.2.2 Follow-up Survey After Study Drug Discontinuation" respectively.

Surveys of subjects for whom "4.2.3 Discontinuation of Study Participation and Termination of the Entire Study" applies will be deemed complete as of the examination at discontinuation, which will be performed as far as is possible.

Table 6-1 Study Procedure and Specimen Collection Schedule

		_	D	uration of study	traatmant	
	P1:-11	:1:6				
	Eligibility assessment examination		Every 4	Every 8 weeks from	Examination at	Final fall
			weeks from Week 4 to	Week 48	completion of study	Final follow-up examination ^b
	examir	lation			treatment ^a /examination at	examination
TT-14		1	Week 48	onward	,	
Visit	0	1	2–13	14-	discontinuation	
Visit window	Within days pr randomi	rior to	±14 days ^c	±14 days ^c	Within the 60 days after declaration of completion of the study ^c Within the 7 days after discontination ^c	Within the 30 to 37 days after the examination at completion of study treatment ^c
Informed consent	X					
IRT entry (entry of subject						
information)	X					
Baseline subject	- X					
characteristics ^d	$\leftarrow X$. →				
IRT entry (entry of						
eligibility assessment		X				
result), randomization						
Study drug administration		+			→ *	→ f
Study drug compliance		+			1	
Height	← X	\rightarrow				
Physical						
examination/medical	← X	\rightarrow	X	X	X	X
interview						
Body weight	← X		X	X	X	X
Blood pressure/pulse rate	← X	\rightarrow	X	X	X	X
Hematology testg	← X		X^h	X	X	X
Blood chemistry testg	← X	\rightarrow	X^h	X	X	X
Endocrinology testg	← X	\rightarrow	X^{h}	X	X	X
Urinalysisg	← X	\rightarrow	X^h	X	X	X
CLcri	← X	←	X^h	X	X	X
12-lead electrocardiogram	← X	,	\mathbf{X}^{j}	X^k	X	X
(ECG)	$\leftarrow \Lambda$. →	N	A-	Λ	А
Head CT or MRI ^l	← X	\rightarrow				
Whether surgery or		_				
hospitalization occurred						
Adverse events		+				m
Efficacy/bleeding events		←				
Concomitant medication	←				→	
Follow-up survey after						
interruption/discontinuatio			-			
n of study drug ⁿ						
Pharmacokinetic blood						
samplingg	\sqcup		Xº			
Blood sampling for PD		X				
indicatorsg	\vdash					
Blood sampling for		X	X°			
biomarker measurementg	\vdash					
PGx banking ^p	1		← ∑	$\zeta^q \rightarrow$		

- a: Will not be performed on subjects withdrawn from the study.
- b: Will be performed in subjects who continue the study treatment, in principle, within a month after notifying their study treatment assignments.
- c: Will be calculated by taking the date of the scheduled visit to be Day 0.
- d: Falling score, frailty assessment, and one-leg standing test with eyes open will be surveyed by the time of Visit 3.
- e: Study treatment will be started on the same date that notification of study drug identifiers is given. Study treatment will be continued until the examination at completion of study treatment, which will be performed within the 60 days after the declaration of completion of the study that is made when the planned number of subjects with primary efficacy endpoint events (stroke and SEE) has been collected.
- f: The study drug will be administered only to subjects who provided consent for the additional study treatment during the period from the examination at completion of study treatment to the final follow-up examination.
- g: These will be measured at the central laboratory.
- h: Will be performed once every 8 weeks (Week 4 to Week 48: Visit 3, Visit 5, Visit 7, Visit 9, Visit 11, Visit 13/Week 48 onward: Visit 14, Visit 15, Visit 16...).
- i: Will be calculated with the Cockcroft-Gault formula.
- j: Will be performed once every 12 weeks (Visit 4, Visit 7, Visit 10, Visit 13).
- k: Will be performed once every 24 weeks (Visit 16, Visit 19, Visit 22...).
- 1: If this is performed within 4 weeks before the day of informed consent as part of a physical examination, the results may be used for the eligibility assessment examination, with the consent of the subject.
- m: During the period from the examination at completion of study treatment to the final follow-up examination, only serious adverse events will be monitored.
- n: Checks on whether serious adverse events have occurred, whether efficacy events have occurred, whether bleeding events have occurred, whether the following drugs have been used: anticoagulants, thrombolytics, antiplatelet drugs, intravenous antiarrhythmics, and acidic NSAIDs, blood pressure/pulse rate (if the subject has made a visit), and laboratory tests determined to be appropriate by the investigator or subinvestigator (if the subject has made a visit. If warfarin is being used, measurement of PT-INR is mandatory) will be conducted every 8 weeks.
- o: Will be performed on Visit 3.
- p: Will be performed only at study sites where it is possible.
- q: Will be performed from Visit 2 onwards.

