4.2.2.2 Follow-up Survey After Study Drug Discontinuation

The investigator or subinvestigator will survey the following items until the examination at completion of study treatment at least every 8 weeks at a visit or by telephone, and will enter the information on the case report form. If the subject cannot be contacted by telephone, surveys will be performed by letter. In the case of subject meeting "4.2.2.1-2) Study Drug Discontinuation Criteria" (withdrawal of consent for the study treatment), the investigator or subinvestigator will also find out whether the subject (or legally acceptable representative) is willing to resume the study treatment, and will enter the results on the case report form.

- 1) Whether any serious adverse events have occurred
- 2) Whether any efficacy events have occurred
- 3) Whether any bleeding events have occurred
- 4) Whether any of the following drugs (including over-the-counter drugs) have been used: anticoagulants, thrombolytic drugs, antiplatelet drugs, intravenous antiarrhythmic drugs, or acidic NSAIDs
- 5) Blood pressure and pulse rate (only if the subject makes a visit)
- 6) Laboratory tests determined to be appropriate by the investigator or subinvestigator (only if the subject makes a visit). However, if warfarin is being administered, measurement of PT-INR is mandatory.

4.2.3 Discontinuation of Study Participation and Termination of the Entire Study 4.2.3.1 Discontinuation of Study Participation Due to Withdrawal by Subject

If a subject (or legally acceptable representative) makes a request to withdraw not only from receiving the study drug but also from participation in the study, including all study procedures or follow-up survey related to the study, the investigator or subinvestigator will promptly withdraw the relevant subject from the study and take the suitable action for the subject in response. The investigator or subinvestigator will also perform the examination at discontinuation and make every attempt to ensure the safety of the subject as far as the subject (or legally acceptable representative) is willing to cooperate, and will enter the date of discontinuation and the reason for discontinuation on the case report form.

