7.2 Secondary Endpoints

For the following endpoints, the time to onset of the initial event observed from randomization up to the examination at completion of study treatment or the examination at discontinuation**** will be assessed. Detailed definitions of individual events are shown separately in the Procedures for the Clinical Efficacy Event Committee and the Procedures for the Clinical Bleeding Event Committee.

- 1) Composite of stroke, SEE, and death due to CV
- 2) Major adverse cardiovascular events (MACE): non-fatal MI, non-fatal stroke, non-fatal SEE, or deaths due to CV or bleeding
- 3) Stroke, SEE, and all-cause mortality
- 4) Net clinical benefit: stroke, SEE, major bleeding, and all-cause mortality
- 5) All-cause mortality

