11.4.2 Efficacy Analysis

11.4.2.1 Primary Endpoint

11.4.2.1.1 Primary Analysis

For the composite endpoint of stroke and SEE observed from randomization up to the examination at completion of study treatment or the examination at discontinuation, \$\$\$\$\$\$ the time to onset of the initial event* will be compared. The treatment group will be compared based on a Cox proportional hazard model with the CHADS₂ score (≤ 2 or ≥ 3) as covariate (significance level 5%, 2-sided, confidence coefficient for estimates: 95%). If any factors affecting the primary endpoint are found in a blinded review before data are

^{§§§§§:} For subjects withdrawn from study participation

locked, these factors will also be considered as covariates.

*: This will apply to all events whether or not the subject receives the study drug. The time to onset of the initial event is defined as the time from the day of randomization to the initial event experienced by a subject. For subjects who do not experience an event during the study, the time to onset of the initial event will be censored at the day of the examination at completion of study treatment, the day of the examination at discontinuation (for subjects withdrawn from study participation) or death, whichever comes first.

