11.4.2.2 Secondary Endpoints

The following secondary endpoints will be analyzed in the same way as primary endpoints.

- 1) Composite of stroke, SEE, and death due to CV
- 2) MACE
- 3) Stroke, SEE, and all-cause mortality
- 4) Net clinical benefit: stroke, SEE, major bleeding, and all-cause mortality
- 5) All-cause mortality

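### After full withdrawal from participation the protocol provides no later vital-status check, so subsequent deaths are not counted in all-cause mortality, a secondary endpoint

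*Combined protocol and SAP*

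**What the plan says.** The protocol has two levels of stopping.

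- **Drug only (Sections 4.2.2.1 and 4.2.2.2).** A subject who refuses the drug but agrees to the follow-up survey is contacted at least every 8 weeks by visit or telephone, or by letter if telephone fails, until the completion examination. The survey covers efficacy events, and Section 6.14 lists all-cause mortality among these.
- **Participation (Section 4.2.3.1).** This applies when the wish of the subject or representative is described as: "withdraw not only from receiving the study drug but also from participation in the study, including all study procedures or follow-up survey". Section 6.1 then states that surveys of such subjects "will be deemed complete as of the examination at discontinuation, which will be performed as far as is possible". The completion examination is not done (Table 6-1, footnote a: "Will not be performed on subjects withdrawn from the study").

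The analysis follows the same boundary. Section 7.2 lists "5) All-cause mortality" and assesses time to first event for every secondary endpoint only as far as the completion examination or, where a subject has withdrawn from participation, the discontinuation examination. Section 11.4.2.2 adds: "The following secondary endpoints will be analyzed in the same way as primary endpoints". Section 11.4.2.1.1 censors event-free subjects at the completion examination, or at "the day of the examination at discontinuation (for subjects withdrawn from study participation) or death, whichever comes first". Section 11.3.3 rules out imputation.

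**The concern.** Death can be learned without a visit or a procedure, so all-cause mortality is the secondary endpoint that can most easily be complete. Here it stops at the moment a subject leaves the study.

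The subjects are at least 80 years old and have at least one bleeding risk. Some are enrolled, and may be withdrawn, by a representative. If leaving tends to follow a decline in health, a bleed or a perceived lack of benefit, the censoring is informative. Mortality would then be understated and, if the link differs between groups, the comparison could be distorted. Death is also a component of the other four secondary endpoints in Section 7.2.

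**Working it through.** **1. The plan's own figure.** Section 11.6 asks for 65 events (hazard ratio 0.5, two-sided 5%, 80% power). Schoenfeld: 4 × (1.960 + 0.842)² / (ln 0.5)² = 65.3, and power at exactly 65 events is 79.8%. The figure reproduces. A vital-status check changes neither it nor the 800 subjects.

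**2. Does any other provision supply deaths after withdrawal?**
- Section 4.2.3.3 has the site record a death when a subject dies, and treats that death as the withdrawal. It does not look for deaths after an earlier withdrawal.
- Sections 4.2.3.2 and 4.2.3.4 follow abnormal findings present at discontinuation, for major deviations and termination of the study.
- Section 9.6.1 follows an adverse event already under way, as far as possible.
- Sections 6.13 and 9.6.2 run serious adverse event monitoring to the final follow-up examination, but Section 6.1 has already closed surveys for this group.

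None amounts to a vital-status check, and any death learned this way would still lie outside the Section 7.2 window.

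**3. How many deaths could be missed.** From the plan: N = 800, 2 years of enrolment and 1.5 further years, so follow-up is uniform on 1.5 to 3.5 years. Assumed, because the documents give no rates: constant and independent hazards of withdrawal from participation (w) and death (m).

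Let F(h) be the average of 1 − exp(−h·t) over follow-up: F(h) = 1 − [exp(−1.5h) − exp(−3.5h)] / (2h).
- All deaths = 800 × F(m)
- Deaths observed = 800 × m/(m+w) × F(m+w)
- Withdrawals = 800 × w/(m+w) × F(m+w)
- Standard error ratio ≈ √(all deaths / observed deaths)

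For w = 5%, m = 8%: F(0.08) = 0.1804 and F(0.13) = 0.2754. All deaths = 144.3; observed = 800 × 0.6154 × 0.2754 = 135.6; missed = 8.7 (6.0%). Withdrawals are about 85. Standard error ratio = √(144.3/135.6) = 1.03.

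| w per year | m per year | All deaths | Observed | Missed | Share missed | SE ratio |
|---|---|---|---|---|---|---|
| 2% | 5% | 93.7 | 91.3 | 2.4 | 2.5% | 1.01 |
| 5% | 8% | 144.3 | 135.6 | 8.7 | 6.0% | 1.03 |
| 10% | 5% | 93.7 | 82.7 | 11.0 | 11.7% | 1.06 |
| 10% | 12% | 205.9 | 182.6 | 23.4 | 11.3% | 1.06 |

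The range is about 2 to 23 deaths, or 2-12%. Under independence this is lost information only: the Cox hazard ratio and the Kaplan-Meier estimate are not biased.

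**4. If withdrawal is linked to prognosis (a further assumption).** Keep w = 5% and m = 8%, and let the hazard of death be k times higher after withdrawal. Missed deaths = 800 × the average over follow-up t of ∫₀ᵗ w·exp(−(w+m)s)·[1 − exp(−k·m·(t−s))] ds.
- k = 2: 16.2 missed of 135.6 + 16.2 = 151.8 (11%)
- k = 3: 22.8 missed of 135.6 + 22.8 = 158.4 (14%)

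Analysis with censoring at withdrawal still estimates mortality as if the hazard stayed at 8%: 144.3/800 = 18.0%. The true figures are 151.8/800 = 19.0% and 158.4/800 = 19.8%, so mortality is understated by about 1 and 2 percentage points.

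**The case against.** The strongest reply is that withdrawal is not all-or-nothing. Section 4.2.2 already offers a level with no required visit, down to contact by letter. Only subjects who refuse even that reach Section 4.2.3.1, so the affected group is small, and the assumed 2-10%/year may be high for it. Many of this group may also refuse a vital-status check, and consent may be withdrawn at any time. This stands. The deaths computed above are those missed, and the number recoverable is unknown.

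A reader might infer that the trial's mortality comparison is biased. The documents do not support that. No withdrawal rate or reason is given, and the 2-12% range assumes independence, under which only precision is lost. Bias needs informative withdrawal, which is plausible here but not shown.

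A reader might also infer that subjects are never asked about a vital-status check. The consent form and case report forms were not available for this review, so the supportable statement is that the protocol text makes no provision for it.

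Footnote a alone would be weak support, since it concerns only the completion examination. The point rests on Section 6.1 together with the Section 7.2 window and the censoring rule. Deaths after withdrawal lie outside the endpoint as defined, so this is a design weakness and neither a contradiction nor a breach.

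The follow-up of ongoing adverse events in Section 9.6.1 mitigates this in part but does not close the gap.

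**Conclusion.** The point holds within limits. For subjects who withdraw from participation under Section 4.2.3.1, the protocol text ends data collection and censors all-cause mortality at the examination at discontinuation, and nothing provides for a later vital-status check.

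Under assumed rates of withdrawal (2-10%/year) and death (5-12%/year), about 2-12% of deaths are not counted. If withdrawal is unrelated to prognosis, the consequence is a standard error about 1-6% larger. If it is related, mortality is understated (by 1 to 2 percentage points when the hazard of death doubles or triples after withdrawal in the central case), and the comparison could be biased if the relation differs by group.

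This is a low-cost improvement to a secondary endpoint. It does not put the primary analysis in question. The detailed analysis plan that Section 11 refers to was not available, but it could not supply deaths that the protocol does not collect.

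**What to change.** - **Sections 4.2.3.1 and 6.1, with a matching consent-form item:** at withdrawal from participation, record separately whether the subject or representative also declines a vital-status check.
- **For those who do not decline:** when study completion is declared, record alive or dead, with date of death or last known-alive date, from site records, the treating physician or the family.
- **Sections 7.2 and 11.4.2.2:** extend the window for all-cause mortality to include these data, censoring at the last known-alive date. In the composites that include death, use them only as a sensitivity analysis, because stroke, systemic embolism and bleeding after withdrawal remain unknown.
- **Reporting:** give, by group, the number who withdrew from participation, the number who declined the check and the number whose status was obtained.

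The cost is one consent item, one case report form page and one record check or call per withdrawn subject, with no visit or procedure. The downside is minor site work, and subjects who decline are still not covered.
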